6.2.2. PK Parameters

The PK parameters will be summarized descriptively by treatment group in accordance with Pfizer data standards on the PK Parameter Analysis Set, as data permit. *PK parameters, including plasma AUC_{inf} , AUC_{last} , C_{max} , T_{max} , and CL/F , V_z/F , $t_{1/2}$, as data permit, of PF-07081532 will be summarized descriptively by treatment. For AUC_{inf} , a listing of the individual participant ratios (Test/Reference) will be provided. Box and whisker plots for AUC_{inf} will be plotted by treatment.* Missing values will be handled as detailed in Section 5.3.1. Each PK parameter will be summarized by treatment group and will include the set of summary statistics as specified in Table .

Table 2. PK Parameters to be Summarized Descriptively by Treatment

Parameter	Summary Statistics
AUC _{inf} , AUC _{last} , C _{max} , CL/F, V _z /F	N, arithmetic mean, median, SD, %CV, minimum, maximum, geometric mean and geometric %CV
T _{max}	N, median, minimum, maximum
t _{1/2}	N, arithmetic mean, median, SD, %CV, minimum, maximum

Supporting data from the estimation of t_{1/2} and AUC_{inf} will be listed by analyte and group: terminal phase rate constant (k_{el}); goodness of fit statistic from the log-linear regression (r²); the percent of AUC_{inf} based on extrapolation (AUC_{extrap} %); and the first, last, and number of time points used in the estimation of k_{el}. This data may be included in the clinical study report.

6.3. Subset Analyses

There are no planned subset analyses.

6.4. Baseline and Other Summaries and Analyses

6.4.1. Demographic Summaries

Demographic characteristics will be summarized for the enrolled population in accordance with the CaPS.

6.4.2. Study Conduct and Participant Disposition

Participant evaluation groups will show end of study participant disposition. Frequency counts will be supplied for participant discontinuation(s) by treatment. Data will be reported in accordance with the CaPS.

6.4.3. Study Treatment Exposure

Study treatment exposure will be listed.

6.4.4. Concomitant Medications and Nondrug Treatments

All concomitant medication(s) as well as non-drug treatment(s) will be reported in the listings.

6.5. Safety Summaries and Analyses

All safety analyses will be performed on the Safety Analysis Set.

Safety data will be presented in tabular and/or graphical format and summarized descriptively, where appropriate.

6.5.1. Adverse Events

Adverse events will be reported in accordance with the CaPS.

Participant discontinuations due to adverse events will be detailed by treatment. Data will be reported in accordance with the CaPS.

6.5.2. Laboratory Data

Laboratory data will be listed and summarized by treatment in accordance with the CaPS.

6.5.3. Body Weight

Observed value and change from baseline in body weight will be summarized descriptively by treatment.

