Changes in heart rate	
Potential risk is based on the product labeling for the injectable GLP-1R agonists, liraglutide and semaglutide, for T2DM and obesity.
 
Modest increases in HR have been noted in the early clinical studies with PF-07081532, with most values remaining within the normal range.
	
HR is monitored during the clinical study.

Potential Risk of Clinical Significance	Summary of Data/Rationale for Risk	Mitigation Strategy
Declines in body weight	Decreased appetite and body weight loss have been reported for marketed GLP-1R agonists and declines in body weight have been noted at higher doses of PF-07081532.	Weight is collected at multiple timepoints and will be monitored throughout the trial.
Acute gallbladder disease	Potential risk is based on the product labeling for the injectable GLP-1R agonists, semaglutide and liraglutide, for T2DM and obesity.  Acute gallbladder disease has not been observed in the PF-07081532 clinical trial program to date.	Participants with symptomatic gallbladder disease are excluded from this clinical study.  Participants are monitored for AEs and laboratory tests that may suggest development of acute gallbladder disease.
Study Intervention: Itraconazole		
Rare cases of serious hepatotoxicity, including liver failure and death. There have been reports of congestive heart failure. In post-marketing experience, heart failure was more frequently reported in patients receiving a total daily dose of 400 mg although there were also cases reported among those receiving lower total daily doses. Transient or permanent hearing loss has been reported in patients receiving treatment with itraconazole.	Risk based on product labeling.	Multiple oral doses of 200 mg QD for 9 days are administered in this study and pose minimal risk. Participants will be monitored in an inpatient clinical research unit.
Study Intervention: Cyclosporine		

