## 4. STUDY DESIGN

### 4.1. Overall Design

This is a Phase 1, open-label, fixed-sequence, 3-period study to evaluate the effect of multiple doses of itraconazole and a single dose of cyclosporine on the single-dose PK of PF-07081532 in otherwise healthy, overweight or obese adult participants. The 3 study periods will be conducted consecutively without a break.

All participants will provide informed consent and undergo Screening evaluations to determine their eligibility. Screening will occur within 28 days of the first dose of study intervention on Period 1 Day 1. Participants who discontinue from the study before completing all assessments may be replaced at the discretion of the investigator and sponsor.

Approximately 16 participants will be enrolled in the study such that approximately 12 evaluable participants complete the study.

The total duration of participation from the Screening Visit to the F/U telephone contact will be approximately 82 days or 12 weeks, approximately 3 weeks of which will be conducted on an inpatient basis. The 21-day inpatient portion of the study will be conducted as follows:

**Period 1:** Days -1 to 5 (Study Days -1 to 5; participants are admitted to the CRU on Day -1), 40 mg SD PF-07081532 on Day 1;

**Period 2:** Days 1 to 5 (Study Days 6 to 10), 40 mg SD PF-07081532 plus 600 mg SD cyclosporine on Day 1;

**Period 3:** Days 1 to 10 (Study Days 11 to 20; participants are discharged from the CRU on Study Day 20), 200 mg itraconazole QD ×9 days plus 40 mg SD PF-07081532 on Day 4.

A telephone F/U contact will occur 28-35 days from the last dose of study intervention (Period 3, Day 9).

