2.3. Study Design

This is a Phase 1, open-label, fixed-sequence, 3-period study to evaluate the effect of multiple doses of itraconazole and a single dose of cyclosporine on the single-dose PK of PF-07081532 in otherwise healthy, overweight or obese adult participants. The 3 study periods will be conducted consecutively without a break.

All participants will provide informed consent and undergo Screening evaluations to determine their eligibility. Screening will occur within 28 days of the first dose of study intervention on Period 1 Day 1. Participants who discontinue from the study before completing all assessments may be replaced at the discretion of the investigator and sponsor.

Approximately 16 participants will be enrolled in the study such that approximately 12 evaluable participants complete the study.

The total duration of participation from the Screening Visit to the F/U telephone contact will be approximately 82 days or 12 weeks, approximately 3 weeks of which will be conducted on an inpatient basis. The 21-day inpatient portion of the study will be conducted as follows:

Period 1: Days -1 to 5 (Study Days -1 to 5; participants are admitted to the CRU on Day -1), 40 mg SD PF-07081532 on Day 1;

Period 2: Days 1 to 5 (Study Days 6 to 10), 40 mg SD PF-07081532 plus 600 mg SD cyclosporine on Day 1;

Period 3: Days 1 to 10 (Study Days 11 to 20; participants are discharged from the CRU on Study Day 20), 200 mg itraconazole QD × 9 days plus 40 mg SD PF-07081532 on Day 4.

A telephone F/U contact will occur 28-35 days from the last dose of study intervention (Period 3, Day 9).

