3.5.3. Body Weight

Body weight will be measured at times specified in the SoA given in the protocol.

The baseline measurement is the predose measurement on Day 1 of Period 1.

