3.5.5. Electrocardiograms

QT interval, QTcF, PR, QRS and heart rate (HR) will be recorded at each assessment time indicated in the SoA given in the protocol. QTcF will be derived using Fridericia’s heart rate correction formula:

$$\text{QTcF} = \text{QT} / (\text{RR})^{(1/3)} \text{ where RR} = 60/\text{HR} \text{ (if not provided)}$$

The baseline measurement is the latest measurement on Day 1 of Period 1.

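### Body-weight change is reported by treatment from one Period 1 baseline, so the two combination rows are cumulative over two and three PF-07081532 doses

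*SAP*

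**What the plan says.** Body weight is named among the secondary safety endpoints (SAP 2.2). SAP 6.5.3 plans its summary: "Observed value and change from baseline in body weight will be summarized descriptively by treatment". The baseline comes from SAP 3.5.3: "The baseline measurement is the predose measurement on Day 1 of Period 1". No other weight baseline is defined, and nothing says that later changes are cumulative.

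On design, SAP 2.3 says "This is a Phase 1, open-label, fixed-sequence, 3-period study", and Protocol 4.1 adds: "The 3 study periods will be conducted consecutively without a break". Period 1 is "40 mg SD PF-07081532 on Day 1". Period 2 is "40 mg SD PF-07081532 plus 600 mg SD cyclosporine on Day 1". Period 3 is nine daily doses of itraconazole with the third PF-07081532 dose on its Day 4.

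The schedule of activities (Protocol Table 1) has weights at Screening, Day -1, Period 1 Day 5, Period 2 Day 5, Period 3 Day 10 and early termination. None is scheduled on Period 1 Day 1, so the last scheduled weight before dosing is Day -1.

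Protocol 9.3.2 says weight will be summarized by period. The SAP changes this to by treatment, while SAP 2.1 lists no modifications to the protocol's analysis.

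**The concern.** A weight change carries forward: whatever is lost or gained in Period 1 is still in the Period 2 and Period 3 measurements. With one baseline and one fixed order, a row labelled with a combination contains everything that happened before that combination began. The relevant secondary objective is the safety of PF-07081532 alone and together with each inhibitor, so readers will use a by-treatment table to compare the three conditions.

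Weight is also a variable on which readers will look for a drug effect. The protocol's risk table notes that "declines in body weight have been noted at higher doses of PF-07081532", and the study asks whether the inhibitors raise exposure. A gradient produced only by accumulation could be mistaken for a consequence of higher exposure. A weight gain during confinement would equally appear as a gradient in the other direction.

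**Working it through.** The plan gives no figure for weight change, so there is none to reproduce. The check is a count of days and doses, followed by an illustration.

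**Inputs.** Study days from SAP 2.3: Period 1 is Days -1 to 5, Period 2 is Days 6 to 10, Period 3 is Days 11 to 20. The stated 21 inpatient days equal Day -1 plus Days 1 to 20, so there is no Day 0. PF-07081532 is given on Study Days 1, 6 and 14 (Period 3 Day 4 = 11 + 3). Weights are from Protocol Table 1.

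**Step 1: what each row spans, from the Day -1 weight.**

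| Weight | SAP treatment row | Days from Day -1 | PF-07081532 doses | Inhibitor doses by then |
|---|---|---|---|---|
| Period 1 Day 5 (Study Day 5) | PF alone | 5 | 1 | none |
| Period 2 Day 5 (Study Day 10) | PF + cyclosporine | 10 | 2 | 1 cyclosporine |
| Period 3 Day 10 (Study Day 20) | PF + itraconazole | 20 | 3 | 1 cyclosporine, 9 itraconazole |

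Counted from Study Day 1, as SAP 3.5.3 words it, the spans are 4, 9 and 19 days. The dose counts do not change.

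**Step 2: what each row contains.** Let D1, D2 and D3 be the true changes within the three periods. From a single baseline the rows are:

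- PF alone = D1
- PF + cyclosporine = D1 + D2
- PF + itraconazole = D1 + D2 + D3

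**Step 3: illustration with no inhibitor effect (assumed values).**

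- Equal change d per period gives d, 2d, 3d. For d = -0.3 kg: -0.3, -0.6, -0.9. For d = -0.5 kg: -0.5, -1.0, -1.5. For d = -1.0 kg: -1.0, -2.0, -3.0. Reversing the sign of d reverses every row.
- Constant daily rate r gives 5r, 10r, 20r. For r = -0.1 kg/day: -0.5, -1.0, -2.0.
- No trend gives 0, 0, 0.

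The part of the itraconazole row that accrued by the Period 2 Day 5 weight, before any itraconazole, is 2d/3d = two thirds in the first case and 10r/20r = one half in the second.

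**Step 4: the same cases with period-specific changes.** Take Period 1 Day 5 minus Day -1, Period 2 Day 5 minus Period 1 Day 5, and Period 3 Day 10 minus Period 2 Day 5. The intervals are 5, 10 - 5 = 5 and 20 - 10 = 10 days, with one PF-07081532 dose in each.

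- Equal change per period: d, d, d.
- Constant rate of -0.1 kg/day: -0.5, -0.5, -1.0. The last row is still twice the others because its interval is twice as long; per day all three are -0.1.

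Differencing therefore removes the accumulation but not the effect of unequal intervals.

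**The case against.** **It is only labelling.** Treatment and period coincide for everyone, so a by-period table would hold the same numbers; no hypothesis is tested and no between-treatment comparison of weight is planned. All of this is correct, and it limits the weight of the point. But in a descriptive table the label carries the interpretation, and here it names one treatment for a change accrued over several.

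**The period change can be recovered.** Observed values are also summarized, so successive means can be subtracted. That works for the mean if the same people are in each row. About 16 are to be enrolled for about 12 evaluable completers, so rows may differ. The spread of the within-period changes cannot be recovered from the row standard deviations.

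**The direction is unknown.** A reader might infer that the table will show growing loss with each combination, even a fourfold gradient. The documents do not support that. They give no weight-change figure, they link weight decline to higher doses, the dose here is a single 40 mg per period, and confinement intake may reach about 3200 kcal/day. Flat or rising weight is possible.

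**The remedy is imperfect.** Order, diet and confinement stay confounded with treatment, and Period 3 is longer and opens with three days of itraconazole alone. This stands and calls for a caveat. Later-period baselines are also not drug-naive: they fall about 96 h after the previous dose. At the reported mean half-lives without an inhibitor, that is 96/26.50 = 3.6 to 96/18.03 = 5.3 half-lives. A single drug-naive baseline is defensible for a safety summary, which is a reason to keep the cumulative rows.

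**ECG.** A reader might extend the point to ECG, since SAP 3.5.5 says "The baseline measurement is the latest measurement on Day 1 of Period 1". The extension fails: SAP 6.5.5 tabulates ECG change by period and time, so cumulative change is not labelled as a treatment's change. The Period 3 Day 1 pre-dose and Day 10 ECGs are both scheduled time points.

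**Conclusion.** The point holds for body weight. The combination rows are cumulative over two and three PF-07081532 doses, about 10 and 20 days from the Day -1 weight, and cannot be read as change on the named treatment. This follows from the SAP's baseline definition and the fixed sequence and needs no assumption about weight. The SAP also departs from the protocol's by-period summary without declaring it.

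How large any gradient would be, and its sign, cannot be stated from the documents. The multiples of 2 and 3 assume equal change per period; 2 and 4 assume a constant daily rate. A reader should not conclude that a spurious loss will be attributed to itraconazole, only that the table could not separate such an artefact from a treatment effect. The primary pharmacokinetic analysis is untouched; the consequence is confined to one descriptive secondary safety table.

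**What to change.** In SAP 3.5.3 and 6.5.3:

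1. Summarize change from the pre-Period 1 weight by period, as in Protocol 9.3.2, and label it cumulative over the sequence. Name Day -1 as the baseline record.
2. For the by-treatment summary, add period-specific change: Period 1 Day 5 minus Day -1 (PF-07081532 alone); Period 2 Day 5 minus Period 1 Day 5 (with cyclosporine); Period 3 Day 10 minus Period 2 Day 5 (with itraconazole).
3. State the intervals (5, 5 and 10 days) in the table.
4. Footnote that period order, confinement and interval length remain confounded with treatment, and that the Period 2 and Period 3 baselines follow earlier PF-07081532 dosing.
5. If the by-treatment summary is kept, record it in SAP 2.1 as a change from the protocol.

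The cost is a few lines of SAP text and one derived baseline variable. No new weights or visits are needed, and ECG needs no change on this ground.

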6.5.4. Vital Signs

Vital signs data will be listed and summarized by treatment in accordance with the CaPS.

6.5.5. Electrocardiograms

Changes from baseline for the ECG parameters HR, QTcF, PR interval, and QRS complex will be summarized by period and time. The frequency of uncorrected QT values above 500 ms will be tabulated.

The number (%) of participants with maximum postdose QTcF values and maximum increases from baseline in the following categories will be tabulated by period:

Safety QTcF Assessment

Degree of Prolongation	Mild (ms)	Moderate (ms)	Severe (ms)
Absolute value	>450-480	>480-500	>500
Increase from baseline		30-60	>60

Baseline will be pre-dose on Day 1.

6.5.6. Mental Health

C-SSRS and PHQ-9 data will be listed.

7. INTERIM ANALYSES

No formal interim analysis will be conducted for this study. As this is an open-label study, the sponsor may conduct unblinded reviews of the data during the course of the study for the purpose of safety assessment, facilitating PK modeling, and/or supporting clinical development.

Final analysis will follow the official database release. As this will be an open-label study, there is no formal unblinding of the randomization code.

APPENDICES

Appendix 1. SAS Code for Analyses

An example of the PROC MIXED code is provided below:

For the primary objective:

Treatment B (Test) vs Treatment A (Reference)

```
proc mixed data=tab.pk;
  where trt in ("A","B");
  class trt participant;
  model l&var=trt / ddfm=KR;
  random participant / subject=participant;
  lsmeans trt;
  estimate 'B vs A' trt -1 1 /cl alpha=0.1;

  ods 'Estimates' out=est&var;
  ods 'lsmeans' out=ls&var;
  ods 'covparms' out=cov&var;
  ods 'tests3' out=tst&var;
run;
```

Treatment C (Test) vs Treatment A (Reference)

```
proc mixed data=tab.pk;
  where trt in ("A","C");
  class trt participant;
  model l&var=trt / ddfm=KR;
  random participant / subject=participant;
  lsmeans trt;
  estimate 'C vs A' trt -1 1 /cl alpha=0.1;

  ods 'Estimates' out=est&var;
  ods 'lsmeans' out=ls&var;
  ods 'covparms' out=cov&var;
  ods 'tests3' out=tst&var;
run;
```

```
/* Letter assignments for treatments (trt) within the estimate statement above are as follows
A: 40 mg SD PF-07081532
B: 40 mg SD PF-07081532 plus 600 mg SD cyclosporine
C: 200 mg itraconazole QD x9 days plus 40 mg SD PF-07081532
*/
```

Appendix 2. List of Abbreviations

Abbreviation	Term
%CV	coefficient of variation
AE	adverse event
AUC ₂₄	area under the plasma concentration-time profile from time zero to time 24 hours
AUC _{inf}	area under the plasma concentration-time profile from time zero extrapolated to infinite time
AUC _{last}	area under the plasma concentration-time profile from time zero to the time of the last quantifiable concentration (C _{last})
BLQ	below the limit of quantitation
BMI	body mass index
BP	blood pressure
CaPS	Clinical Data Interchange Standards Consortium and Pfizer Standards
CI	confidence interval
C _{last}	predicted plasma concentration at the last quantifiable time point estimated from the log-linear regression analysis
CL/F	apparent oral clearance
C _{max}	maximum plasma concentration
C-SSRS	Columbia Suicide Severity Rating Scale
CSR	clinical study report
ECG	electrocardiogram
EE	ethinyl estradiol
HR	heart rate
k _{el}	the terminal phase rate constant calculated by a linear regression of the loglinear concentration-time curve
LE	levonorgestrel
LLQ	lower limit of quantitation
MD	multiple dose
mg	milligram
MHP	mental health professional
MR	metabolite to parent ratio
MRAUC _i _{nf}	1-hydroxymidazolam AUC _{inf} /midazolam AUC _{inf} ; 5-hydroxyomeprazole AUC _{inf} /omeprazole AUC _{inf}
N/A	not applicable
NC	not calculated
ND	not done
NS	no sample
OC	oral contraceptive
PHQ-9	Patient Health Questionnaire-9
PK	pharmacokinetic(s)
PR	pulse rate

Abbreviation	Term
QD	once daily
QRS	Combination of Q-, R- and S- wave on an electrocardiogram representing ventricular depolarization
QTc	corrected QT
QTcF	corrected QT (Fridericia method)
RR	R-R interval from ECG
SAP	statistical analysis plan
SD	single dose; standard deviation
SoA	schedule of activities
$t_{1/2}$	terminal elimination half-life
T2DM	type 2 diabetes mellitus
TEAE	treatment emergent adverse event
T_{\max}	time to C_{\max}
V_z/F	apparent volume of distribution
